NCT06338462

Mobile Health and Oral Testing to Optimize Tuberculosis Contact

Tracing in Colombia

Approved July 1 , 2023

Aim 2: To design and iteratively adapt an mHealth strategy for implementing contact tracing optimized for feasibility, acceptability, usability, and appropriateness. We hypothesize that we can refine an mHealth contact tracing package over several cycles of community-engaged design. We will adapt existing client-centered educational and engagement materials for delivery using WhatsApp-embedded 1) interactive client surveys (i.e., “bots”) 2) instructional videos, and 3) video calls. We will introduce these in a single-arm pilot implementation trial enrolling 160 households over one year, with each quarter allowing two months to recruit 40 households and one month to refine strategy components. We will assess feasibility, acceptability, usability, and appropriateness in quantitative exit surveys and 10 key informant interviews with cases and contacts per design cycle. During each round of data collection, we will prepare and distribute rapid summaries of interviews and surveys to a stakeholder focus group and then apply nominal group technique, a community-engaged design methodology, to elicit and select stakeholder modifications to the mHealth contact tracing package. As a secondary outcome, we will quantify changes in contact tracing uptake, completion, retention, and yield.

Introduction. Contact tracing is a complex intervention that is challenging to implement in resource-constrained health settings. While cultures and contexts vary, common barriers exist that are correctable with streamlined, client-centered approaches to screening, testing, and linkage to care delivered in a safe, timely, and convenient location. The pandemic has shifted community norms and preferences towards tele-health⁸⁶, and we now propose to develop and optimize an mHealth-facilitated TB contact tracing strategy to improve reach, yield, timeliness, and retention in contact tracing. If successful, this research will inform TB contact tracing efforts in similar settings in Latin America where marginalized populations cannot access TB services. To achieve this, we will test the hypothesis that an optimized mHealth contact tracing package can be achieved through cycles of community-engaged design. Specifically, we will determine qualitatively if video calls increase opportunity to engage in contact tracing; if instructional videos improve motivation of cases and contacts to engage in tracing and capability of contacts to produce a respiratory sample; and, finally, if an automated assistant (“chatbot”) can assist health workers in providing more timely and flexible services to households. The expected outcome of this study is a feasible, acceptable, usable, and appropriate mHealth implementation package for a future household randomized, controlled implementation trial to evaluate implementation effectiveness, fidelity, and cost.

Study Design and Setting. We propose multiple methods studies to achieve our design objectives. First, we will carry out an adaptive single-arm preliminary implementation trial within the SPH contact tracing program to pilot and adapt mHealth innovations. Second, we will conduct a nested qualitative study to collect key informant interviews with cases and contacts on their experiences with mHealth tracing. Third will apply nominal group technic (**NGT**) with stakeholders to review the implementation data and to elicit and vote on suggestions on refining mHealth components. We will carry several iterative design cycles, each with one implementation stage and one adaptation stage, after a 3-month run-in period.

Implementation stage: The initial mHealth strategy will be delivered to index patients and identified contacts of index patients. We will collect exit surveys on early implementation outcomes (feasibility, acceptability, appropriateness, usability) and interview 15 purposively selected case and contacts in participating households.

Adaptation stage. Results from the implementation stage will inform modification and adaptation of the mHealth package using NGT⁸⁷ with stakeholders from the community, households, health workers, SPH, and researchers. Outcomes of this phase are modifications of the mHealth package, based on stakeholder suggestions and votes. We will document these using the model for adaptation design and impact (MADI).⁸⁸

Participants. We will include 240 newly diagnosed TB patients (*i.e.*, 20/month) and their household contacts reported in the National Epidemiological Surveillance databases (SIVIGILA) database and living in Cali. Stakeholders will include SPH personnel responsible for TB contact tracing activities (logistics, human resources, coordination, schedulers, visitors), health providers (doctors and nurses in PHCs), and TB nurses in PHCs.

Recruitment. Contact tracing. Cases and enumerated household contacts will be invited to WhatsApp chat with the SPH outreach worker using secure customer relations management software and invited to a intake call where verbal consent will be obtained. Client Interviews. After verbal consent, we will purposively sample 15 index patients and contacts for exit interviews per design cycle. Stakeholder Panel. Participants will be formally invited after soliciting names from TB advocacy groups, the SPH, and Alianza-TB; we will obtain verbal consent to participate in each nominal group. The group consist on members of the academy, public health sector, and members o the community.

Procedures. Design and delivery of implementation packages. The proposed components are targeted to barriers identified in previous collaborative research with the SPH. SPH will assign two TB outreach workers to pilot and adapt existing contact tracing materials for mHealth with the SPH communications team. Below, we specify the mHealth intervention components that will be delivered as part of routine contact tracing, using the Behavior Change Wheel framework and the Template for Intervention Description and Replication.

Chatbot-assisted client interactions.

Description

Design of first version:

The design of the first version was conducted based on the preliminary results of a systematic literature review on outcomes of Automated Conversational Agents on infectious diseases healthcare services, the team of researchers joined with the technical local providers develop an initial conversational flow that provided the first set of services to the taget users (initaly index cases).}

Capabilities

Capturing Information:

Providing Information:

Decision Making (Automatic scheduling):

User engagement and support

Articulation with field activities

Measurement of implementation outcomes. First, after tracing interviews with cases and contacts, SPH workers will administer AIM, FIM, IAM, and system usability scale survey instruments, all locally adapted and translated.⁸⁹ Second, research staff with qualitative interview expertise will conduct brief key informant interviews with a purposive (age, gender, race/ethnicity) sample of ~15 cases and contacts per cycle (45 total) to elicit client perspectives on the mHealth strategy. We will record all interviews and have them professionally transcribed. Third, we will prepare rapid interview summaries from deductive field notes structured using Proctor's early-stage implementation outcomes⁹⁰ (feasibility, acceptability, appropriateness) plus usability, with illustrative quotes. We will share these with the stakeholder panel for review in advance of the NGT focus group discussions.

Adaptation stage procedures. Using NGT, stakeholders will suggest adjustments to the mHealth components.⁹¹ Briefly, participants will review case and contact interview summaries and, in open round-robin discussion, present possible adjustments and rationale. Finally, participants will engage in concealed rank-choice voting on the proposed adjustments. The 3 highest-ranked innovations will be revealed and implemented during the next design cycle, after they are operationalized by the design team.

Sample Size and Statistical Analysis Plan. *For quantitative analyses of implementation outcomes.* Sample size is based on convenience given our formative objectives. We will include 240 households over 1 year (20 index TB patients and contacts per month), a feasible target. We will summarize quantitative FIM, AIM, IAM, & usability scores by client type (cases, contacts) and construct general linear mixed models (GLM) to determine the effect of each design cycle on scores, with household as a random effect. As an exploratory analysis, we will construct GLM models (logit link, household as a random effect) of tracing uptake, completion, yield, linkage to prevention, retention, using prior definitions.¹²

For qualitative analyses. Assuming a homogeneous population, we expect to reach code saturation with a minimum of 12 interviews⁹², so we will plan 15 interviews per cycle and adjust based on thematic analysis.⁹³ Qualitative recordings of interviews and focus groups, field notes, and programmatic materials will be collated and analyzed using RADA, a rapid analysis technique.⁹⁴

Potential challenges and alternative approaches. Including 240 households may appear ambitious, but since this data will be collected passively during routine tracing, the marginal research cost of additional households is small, and more repetition with the mHealth strategy will accelerate design insights. In case a smaller target becomes necessary, we anticipate still having enough information to meet design objectives. Novel technologies rapidly evolve, and adjustments may be necessary, so we have included commercial partners to assist us in rapidly adapting to available technologies. Some clients may prefer traditional visits over telehealth visits, but our hybrid human-mHealth strategy allows greater flexibility to meet patients where they are.

Expected Outcomes. The expected outcome of Aim 2 is an optimized mHealth strategy for TB contact tracing with enhanced feasibility, acceptability, usability, and appropriateness, to prepare for a larger household-randomized, controlled implementation trial. We will also acquire a preliminary understanding of the impact and effectiveness of the new strategy. We will have

protocols for training on and implementing a digital contact tracing strategy, including digitalized educational materials and a parametrized, automated chatbot. We will also advance the understanding of the ethics and safety of using commercial chat applications for public health data on individuals and contribute a model for more equitable design of implementation strategies.

TIDieR Components Summary

Component	Engagement and Linkage	Education and Information	Data Capture	Automatic Scheduling	Agent Support Transfer	Coordination with Field Activities
Rationale/Goal	Identify and link TB cases and contacts to TB cases and their contacts for early and effective disease management.	Educate TB cases and contacts about symptoms, prevention, and treatment to improve disease adherence and disease management.	Capture data on diagnosis perception, confirm personal data, and monitor treatment adherence and symptoms.	Facilitate scheduling of home visits and calls to ensure continuity of patient and contact care.	Provide human support or chatbot support for unresolved user queries, and ensure personalization.	Integrate chatbot work with field activities for coordinated queries, and ensure TB care.
Procedures and Frequency	Automated messages and home visits by health workers. Updated weekly.	Chatbot contacts cases and contacts via ongoing TB education on-demand, updated periodically.	Chatbot collects data on diagnosis perception, personal data, treatment requirement s, and symptom tracking.	Chatbot schedules visits and calls based on health staff availability and user preferences, with reminders.	Chatbot transfers unresolved queries to support agents in real-time during office hours.	Chatbot coordinates with field staff to update case and contact information and schedule visits weekly.
Agent	Chatbot acts as the primary contact agent using data provided by the Health	Chatbot acts as an educational agent with approved knowledge from health professionals.	Chatbot acts as the main agent for data collection, transferring to health staff when needed.	Chatbot schedules visits using a synchronized database with health staff calendars.	Chatbot acts as the first point of contact, linking transferrin patients/contacts and field interactio ns to	Chatbot acts as the digital link between patients/contacts and field staff.

Component	Engagement and Linkage	Education and Information	Data Capture	Automatic Scheduling	Agent Support Transfer	Coordination with Field Activities
Mechanisms	Departmentalized automated personalization confirming diagnosis and providing initial information.	Automated messages confirming diagnosis and providing initial information.	Automated messages and responses to specific queries.	Automated questionnaires and data logs.	Integration with data management.	Real-time transfer system and notifications for support staff.
Barriers Addressed by Intervention	Integration with data management systems for tracking responses and updates.	Chatbot provides links to additional resources and multimedia educational materials.	Chatbot alerts for additional follow-up by health staff.	Chatbot systems and reminder notifications.	Chatbot provides interaction summaries to ensure care continuity.	Integration of databases and systems for task management.
Possible Adaptations and Improvements	Lack of timely case identification and difficulties in linking patients to follow-up processes.	Inconsistencies in data collection and difficulties in access to reliable TB information.	Misinformation and lack of access to reliable TB information.	Difficulties in coordinating and scheduling appointments.	Limitations in chatbot capabilities.	Lack of coordination and communication between complex digital work queries and user needs.
	Adapting messages for different languages and literacy levels, including personalization.	Customizing educational content based on user risk profiles, integrating multimedia (videos, infographics).	Incorporating more detailed surveys, personalized follow-up schedules, and user interface improvements.	Personalizing scheduling options, incorporating real-time confirmations, and flexible	Continuous training for support staff, incorporating real-time confirmations, and flexible	Enhancing data synchronization, providing mobile tools for field staff, interacting and conducting interfaces, periodic feedback

Component	Engagement and Linkage	Education and Information	Data Capture	Automatic Scheduling	Agent Support Transfer	Coordination with Field Activities
	ed), and reminders offering and direct contact options with health staff for greater support.	ts to facilitate information in the user's preferred language.	data capture.	rescheduling.	follow-up options post- interaction.	sessions to improve integration.

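### Does it matter that the protocol plans no implementation stage after the last stakeholder vote?

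*Protocol*

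**What the plan says.** Study Design and Setting describes several design cycles, "each with one implementation stage and one adaptation stage". The Implementation stage paragraph places the exit surveys and interviews in the first of these. The Adaptation stage paragraph lets those results inform the nominal group vote and adds: "Outcomes of this phase are modifications of the mHealth package, based on stakeholder suggestions and votes". The modifications are to be documented with a named adaptation model (MADI).

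Adaptation stage procedures sets the rule for the winning proposals: "The 3 highest-ranked innovations will be revealed and implemented during the next design cycle, after they are operationalized by the design team".

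The Aim 2 paragraph gives the same order on a calendar, with "each quarter allowing two months to recruit 40 households and one month to refine strategy components". It also repeats the vote throughout: "During each round of data collection, we will prepare and distribute rapid summaries of interviews and surveys to a stakeholder focus group", followed by the nominal group method "to elicit and select stakeholder modifications to the mHealth contact tracing package".

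The Introduction names the product: "a feasible, acceptable, usable, and appropriate mHealth implementation package for a future household randomized, controlled implementation trial". The Sample Size and Statistical Analysis Plan section models survey scores by design cycle, with household as a random effect.

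**The concern.** Read literally, the rule has nothing to act on after the last vote, because no cycle follows it. Surveys and interviews belong to the implementation stage, so the last three changes would be chosen and perhaps built into the package without any client being asked about them in this study.

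At stake is the link between the scores and the product. If those changes go into the package for the later randomised trial, the last-cycle scores describe a version that differs from it by up to three changes. A reader could then take those scores as describing the final package.

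**Working it through.** **Order of stages.** The Adaptation stage paragraph has implementation results feeding the vote, and the Aim 2 paragraph puts refinement after recruitment. Each cycle therefore ends with the vote. No closing implementation stage appears anywhere in the protocol.

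**Number of cycles, C.**
- Measurement of implementation outcomes gives about 15 interviews per cycle and 45 in total: 45 / 15 = 3 cycles.
- The Aim 2 paragraph gives four quarters of 40 households, and 4 × 40 = 160 reproduces its stated total. If each quarter is one cycle (an assumption), C = 4.

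**Changes fielded.** With three changes per vote, 3C are chosen, 3(C − 1) reach a later cycle and 3 do not. The share not fielded is 3 / 3C = 1 / C.

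| | C = 3 | C = 4 |
|---|---|---|
| Chosen | 9 | 12 |
| Fielded in a later cycle | 6 | 9 |
| Not fielded | 3 (33%) | 3 (25%) |

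The percentage is only the reciprocal of the number of cycles. It measures neither bias nor the importance of the changes.

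**Calendar.** On the Aim 2 timetable, recruitment falls in months 1–2, 4–5, 7–8 and 10–11, and refinement in months 3, 6, 9 and 12. None of the 160 households would follow the last refinement. This count is not firm. Participants and the sample size section plan 20 households a month for a year, 12 × 20 = 240, which leaves no month free of recruitment and does not date the last vote. That difference between the two timetables is a separate matter.

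**Effect on the planned estimates.** Each cycle's scores come from its own implementation stage, and the last vote comes after all of them. It cannot alter a score already collected, so the per-cycle comparison is unaffected for every version that was surveyed.

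**What the other ending would cost.** The last cycle's interviews can shape the package only through the last vote. They are 15 of 45 (33%) or, at "10 key informant interviews with cases and contacts per design cycle" over four cycles, 10 of 40 (25%). Stopping after the last implementation stage would leave them without effect on the package.

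Adding a closing stage at 15 interviews would raise the total from 3 × 15 = 45 to 4 × 15 = 60. At 10 per stage over four cycles, it would rise from 40 to 5 × 10 = 50. The households needed are not given; 40 to 60 is an assumed range (two to three months at 20 per month). The closing stage would then raise the same question: its findings are either acted on without a further survey or not acted on.

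**The case for a change.** The best case for a change is that the package is what the study delivers. Expected Outcomes presents it as improved on the four early implementation outcomes, yet the version after the last vote is never surveyed. The later trial may not close the gap, since the Introduction gives its aims as effectiveness of implementation, fidelity and cost. Staff at the last vote would find a rule with no next cycle to apply it to. A few sentences would settle this without adding a household or an interview.

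The factual core stands: the last three changes have no planned measurement on either cycle count, and no text makes an exception for them.

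The rest does not make a defect. A rule about the next cycle, read in the ordinary way, applies wherever there is one. At the end it is silent, which is different from conflicting with the other text. The output of the adaptation stage is itself defined as modifications of the package, so the natural reading is that the last ones enter it, with the adaptation record showing what they were. Scores are already tied to cycle, and hence to the version fielded. Which version is randomised later is for that trial's protocol to fix. The proposed sentences would record a policy but would alter no procedure, number or result.

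**Conclusion.** No change to the plan is needed. Up to three changes (three of nine, or three of twelve) may enter the final package without a survey or interview in this study. This rests on the stated order of stages and on three changes per vote, and it holds whether there are three cycles or four. It is an ordinary feature of a finite iterative design and a fair trade-off in a formative pilot whose sample size is set by convenience. It biases no planned estimate.

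The remaining point is one of reporting, which analysts can be expected to handle: the last-cycle scores describe the version used in that cycle, and any changes from the last vote carried forward were not surveyed. A month-by-month count of unmeasured households should be used only with the caveat that it rests on the Aim 2 timetable.

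### The protocol gives two incompatible enrolment plans (160 households in 8 recruiting months, or 240 in 12), and does not tie the start of a design cycle to the date its changes go live

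*Protocol*

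**What the plan says.** **Enrolment.** The opening Aim 2 paragraph describes a single-arm pilot "enrolling 160 households over one year, with each quarter allowing two months to recruit 40 households and one month to refine strategy components". The Participants section says "We will include 240 newly diagnosed TB patients", at 20 a month. The Sample Size and Statistical Analysis Plan says "We will include 240 households over 1 year (20 index TB patients and contacts per month), a feasible target". All three are current text; none belongs to an amendment log.

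**Cycles.** Study Design and Setting plans "several iterative design cycles, each with one implementation stage and one adaptation stage, after a 3-month run-in period".

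**Go-live.** Adaptation stage procedures says of the changes chosen by vote: "The 3 highest-ranked innovations will be revealed and implemented during the next design cycle, after they are operationalized by the design team". The Adaptation stage paragraph has the modifications documented under MADI. It does not mention a go-live date or a record of which version a respondent received.

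**Measurement and model.** Under Measurement of implementation outcomes, "after tracing interviews with cases and contacts, SPH workers will administer AIM, FIM, IAM, and system usability scale survey instruments". The analysis section will "construct general linear mixed models (GLM) to determine the effect of each design cycle on scores, with household as a random effect".

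**The concern.** There are two separate problems.

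First, the household total and the enrolment calendar are each stated in two ways. The two calendars differ on whether households are recruited while the package is being refined, so the discrepancy is more than a mistyped total. Anyone planning staff, surveys or the analysis has to guess which calendar applies.

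Second, the model uses the design cycle as its term, while the thing that changes between cycles is the package. The two coincide only if each round of changes is in use from the first respondent of its cycle. The go-live sentence allows changes to arrive during a cycle. Respondents surveyed before that point would be scored on the previous version but counted in the new cycle. The contrast for that round would then be diluted, and part of its effect would be credited to the next round. The model is the protocol's stated quantitative analysis of its implementation outcomes, so what its coefficient means should be settled in advance.

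**Working it through.** **1. Reproducing the two totals.**
- Opening Aim 2 paragraph: 4 quarters × 40 households = 160. Recruiting months: 4 × 2 = 8. Rate: 160 / 8 = 20 per month.
- Participants and Sample Size: 20 per month × 12 months = 240. Equivalently, 240 / 20 = 12, so every month of the year must enrol.

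Each total follows from its own calendar, and both use the same monthly rate. The difference is 240 − 160 = 80 = 4 refinement months × 20. Reaching 240 in 8 recruiting months would need 240 / 8 = 30 per month, a rate stated nowhere.

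The place of the run-in is also open. If the 3-month run-in lies inside the year and enrols nobody, 20 × 9 = 180, which matches neither total.

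**2. What a late go-live does to the cycle contrasts.** Let m_k be the true mean score under version k, and d_k = m_k − m_(k−1) the change brought by the round that produced version k. Let q be the share of each cycle after the first that is surveyed before its changes go live. Cycle 1 uses the initial package throughout. Assume the changes of a round go live together and are in use by the end of their cycle. Then, for k ≥ 2:

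- mean score in cycle k = (1 − q) m_k + q m_(k−1)
- cycle 2 minus cycle 1 = (1 − q) d_2
- cycle 3 minus cycle 2 = (1 − q) d_3 + q d_2

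The documents do not give q, so it is shown over an assumed range:

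| q | Weight on the round's own change | Weight carried from the previous round |
|---|---|---|
| 0 | 1.00 | 0 |
| 1/6 | 0.83 | 0.17 |
| 1/3 | 0.67 | 0.33 |
| 1/2 | 0.50 | 0.50 |

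The first cycle contrast has only the middle column. Later contrasts have both.

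**3. What q means in time.** Cycle length is itself an assumption: the Aim 2 paragraph implies four quarterly cycles, while the interview count under Measurement of implementation outcomes implies 45 / 15 = 3 cycles. With even enrolment:
- Three-month cycle enrolling throughout (60 households): a half-month delay gives 10 / 60 = 1/6, and a one-month delay gives 20 / 60 = 1/3.
- Four-month cycle enrolling throughout (80 households): a one-month delay gives 20 / 80 = 1/4, so weights of 0.75 and 0.25.
- Aim 2 calendar with a refinement month (40 households per cycle): if building overruns that month by half a month and recruitment starts on time, 10 / 40 = 1/4.

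The last line shows that the mixing depends on the go-live date. A refinement month makes it less likely but does not exclude it, and continuous enrolment does not by itself produce it.

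**The case against.** **Continuous enrolment does not cause the mixing.** A reader might infer that, with enrolment in all 12 months, every household enrolled during an adaptation stage is misclassified. The documents do not support this. Study Design and Setting defines a cycle as an implementation stage plus an adaptation stage, so a household enrolled in the adaptation stage of cycle k receives version k and belongs to cycle k. Cycle and version still agree. The remark that "since this data will be collected passively during routine tracing" does not help that reading either: it argues that extra households cost little, and does not describe enrolment during adaptation. This objection stands in full.

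**The mismatch is not shown.** The go-live sentence can be read as making operationalization a precondition for use in the next cycle, and the Adaptation stage paragraph lists finished modifications as the output of that stage. On that reading q = 0. This stands as a limit: the wording permits a late go-live but does not establish one.

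**Coding belongs in the SAP, and little hangs on the contrast.** How changeover respondents are coded is commonly left to the SAP, which is not at hand. The study is formative, the sample is one of convenience, stakeholders review interview summaries before they vote, and no decision threshold is tied to a cycle contrast. The effect of a cycle as actually run is also a legitimate programme-level quantity. These points lower the weight of the second problem to a clarification. They do not remove it, because the protocol itself names the cycle as the model term and leaves the changeover open. A small or convenience sample excuses low precision, but not an unclear meaning of the estimate.

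None of this touches the two enrolment plans, which cannot both be true.

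**Conclusion.** The enrolment contradiction is established by the protocol's own figures: 160 households in 8 recruiting months against 240 in 12, a gap of 80 households. It should be corrected.

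The mismatch between cycle and version is possible and unresolved. Its size depends wholly on q, which the documents do not give. There is no effect at q = 0. At q = 1/6 the first contrast keeps 0.83 of the true change and 0.17 is carried into the next; at q = 1/3 the figures are 0.67 and 0.33. This rests on even enrolment, the same q in each later cycle, and the changes of a round going live together. Where two successive rounds have equal effects, the later contrast is unaffected, since (1 − q) d + q d = d; the first contrast is still diluted.

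The stronger conclusion, that the cycle effects will be biased or that a known fraction of households will be misassigned, does not follow from the documents.

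**What to change.** 1. Reconcile the opening Aim 2 paragraph, Participants, and Sample Size on one enrolment calendar. Say whether recruitment continues during adaptation and whether the run-in falls inside the year, and give the household total that follows.

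2. Settle the changeover in one of two ways:
   - state in Adaptation stage procedures that a new cycle begins only when its changes are live; or
   - enter the go-live date of each round of changes in the MADI record already planned, and replace design cycle in the model with the package version in use at each respondent's tracing interview. The field belongs to the respondent, because members of one household may be surveyed at different times. The household random effect stays.

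**Cost.** Wording in a few sections and, for the second option, one date per round of changes and one field per respondent. No added households, visits or surveys. The dates should be recorded as the changes are made, since nothing in the protocol would otherwise ensure that they can be recovered. The downside of version coding is that a version in use only briefly may have few respondents and a wide interval. Neither option separates the effect of the changes from a trend over calendar time, which remains a limit of a single-arm design.

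### The stated model for the effect of design cycle leaves out client type, so a change in the case/contact mix of respondents would enter the cycle coefficient; adding client type is a minor improvement at no cost

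*Protocol*

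**What the plan says.** Under Measurement of implementation outcomes, the protocol has both cases and contacts complete the acceptability, feasibility, appropriateness and usability instruments after their tracing interviews. The Sample Size and Statistical Analysis Plan section then describes the analysis in one sentence with two parts: "usability scores by client type (cases, contacts) and construct general linear mixed models (GLM) to determine the effect of each design cycle on scores". The first part splits the summary of the scores by client type. The second is the model, which also has a random household effect. No other model term is named.

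The design section describes the study this way: "we will carry out an adaptive single-arm preliminary implementation trial within the SPH contact tracing program". Newly diagnosed patients and their households enter month by month, so each cycle is made up mainly of different households and has no concurrent comparison group. On size, the plan says "We will include 240 households over 1 year (20 index TB patients and contacts per month), a feasible target", and on its basis, "Sample size is based on convenience given our formative objectives".

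Age and gender appear in connection with the qualitative interviews only, which use a "purposive (age, gender, race/ethnicity) sample of ~15 cases and contacts per cycle".

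**The concern.** The plan treats client type as important enough to split the summary by it, but does not carry it into the model meant to isolate the effect of each cycle. With no randomisation and no concurrent control, nothing in the design balances the respondents of one cycle against those of the next. The household random effect does not do it either: the cycle contrast is mainly between households, whereas client type varies within them.

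At stake is the interpretation of the cycle coefficient. If contacts make up a larger share of respondents in a later cycle and tend to score lower (or higher) than cases, the model would show scores moving even though neither group's score had changed.

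**Working it through.** **The plan's own figures.** 20 households per month × 12 months = 240, as stated. About 15 interviews per cycle and 45 in total imply 45/15 = 3 cycles, hence 240/3 = 80 households per cycle. The quarterly schedule in the opening Aim 2 paragraph implies 4 cycles, hence 240/4 = 60. I use 60 to 80. (That paragraph also gives 160 households, 40 per quarter. Fewer households would widen the intervals below and leave the distortion unchanged.)

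**Distortion.** Without client type in the model, the cycle contrast is off by approximately

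gap between contacts and cases × change in contact share between cycles.

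The mixed model weights households somewhat differently from a simple mean, so this is an approximation. Neither input is in the documents. Assuming a gap of 0.4 to 0.6 SD and a shift of 10 to 15 points:

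- 0.4 × 0.10 = 0.04 SD
- 0.6 × 0.15 = 0.09 SD

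If either factor is zero, so is the distortion.

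**Precision of a cycle difference.** With n households per cycle, m respondents per household and intra-household correlation ICC (m and ICC assumed), the 95% half-width in SD units is 1.96 × √(2 × (ICC + (1 − ICC)/m)/n).

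- n = 60, m = 1: 1.96 × √(2/60) = 0.358
- n = 80, m = 4, ICC = 0.3: 1.96 × √(2 × 0.475/80) = 0.214

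The first is a limiting case, since one respondent per household leaves little room for a varying mix; n = 60, m = 2, ICC = 0.3 gives 1.96 × √(2 × 0.65/60) = 0.289, inside the range. The distortion is thus between 0.04/0.358 = 11% and 0.09/0.214 = 42% of the half-width.

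**Does adding client type remove it?** A simulation with no true cycle effect (3 cycles of 80 households, ICC 0.3, 40 runs per setting, so rough) used a deliberately larger shift. With contacts 0.4 SD below cases and their share rising from about 19% to 50%, the mean false contrast of cycle 3 against cycle 1 was −0.14 SD without client type and −0.02 SD with it. With the same gap and a constant 50% share it was about +0.02 SD either way.

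**Could varying household size alone shift the mix by 10 points?** The contact share is K/(1 + K), where K is the mean number of contacts per household, so the SD of its difference between two cycles is about √2 × (SD of contacts/√n)/(1 + K)². Assumed values:

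- mean 3, SD 2: 0.023 at n = 60, 0.020 at n = 80
- mean 1.5, SD 1.5: 0.044 at n = 60, 0.038 at n = 80

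A 10-point difference is then at least 0.10/0.044 = 2.3 SDs away. Chance variation gives shifts of about 2 to 4 points; 10 to 15 points would need a systematic change in who responds.

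**Gain in precision.** If covariates explained 10% of the variance at both levels, the standard error would fall by 1 − √0.9 = 5%. Client type varies within households. If the whole 10% is within-household, then at ICC 0.3 and m = 4 the factor is √((0.3 + 0.6/4)/(0.3 + 0.7/4)) = √(0.45/0.475) = 0.973, a gain of about 2.7%.

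**The case against.** The strongest reply is that one sentence on a formative analysis is being read too closely. The text never says that cases and contacts are pooled or that the model is unadjusted, and a separate analysis plan could add covariates. That is fair as a caution: a reader should not infer a decision against adjustment. But the section carries the title of a statistical analysis plan and names the outcome, the cycle effect and the random effect, so the model as stated can be reviewed and improved.

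Four stronger readings are tempting, and the documents do not support them.

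- *The mix will shift materially.* No section documents such a shift. The remark that the chatbot's first version was aimed initially at index cases concerns its target users, not who answers the scales; the Implementation stage text delivers the initial strategy to index patients and contacts alike. Imbalance from household size is mostly chance, which belongs to sampling error rather than bias.
- *Age and gender should be added at no cost.* They are named only for choosing interviewees. Nothing says that they are recorded for every survey respondent.
- *The tracing models have the same fault.* For these the plan says "we will construct GLM models (logit link, household as a random effect) of tracing uptake, completion, yield, linkage to prevention, retention", using earlier definitions that are cited but not shown. Whether cases and contacts both enter those models cannot be judged.
- *The cycle coefficient drives the adaptations.* It has no stated role there. Adjustments come from stakeholder review of interview summaries and concealed ranked voting.

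One further objection stands in part. If a better package brings in more contacts, the mix is itself partly a result of the package, and the adjusted contrast alone would hide that. This is a reason to report the respondent counts alongside it.

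**Conclusion.** The point holds as a minor one. As stated, the score model has no term for client type, and any difference in case/contact mix between cycles, combined with a difference in how the two groups score, passes into the cycle coefficient. The 0.04 to 0.09 SD rests wholly on the assumed gap and shift, and the half-widths on assumed household correlation and respondents per household. No confirmatory claim or adaptation rule depends on the coefficient. The case for acting is that client type must already be known for the planned summary, so the protection is free; the likely gain in precision is small and is not the reason to do it.

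**What to change.** In the Sample Size and Statistical Analysis Plan section, state each score model as: design cycle and client type (case or contact) as fixed effects, household as a random effect. Report cycle means at a common client-type mix, for example that of the whole study; in this additive model the difference between cycles does not depend on the mix chosen. Give the number of cases and contacts responding in each cycle next to the estimates. Add age and gender only if they are recorded for all survey respondents. No change to the logit tracing models is asked for here.

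The cost is a change of analysis wording. No new data are needed for client type, and sample size and procedures stay as they are.
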